6 STUDY ENDPOINTS

6.1 Efficacy and Pharmacodynamic Endpoints

6.1.1 Primary Efficacy Endpoint

Absolute change in percent predicted forced expiratory volume in 1 second (ppFEV₁) from baseline at Week 4

6.1.2 Secondary Efficacy and Pharmacodynamic Endpoints

The key secondary efficacy endpoints are as follows:

- Absolute change in sweat chloride (SwCl) from baseline at Week 4

- Absolute change in CF Questionnaire-Revised (CFQ-R) respiratory domain score from baseline at Week 4

6.2 Safety Endpoints

Safety and tolerability will be evaluated via the following endpoints:

- Adverse events (AEs)
- Clinical laboratory values
- Standard 12-lead ECGs
- Vital signs
- Pulse oximetry

7 STUDY DESIGN

7.1 Overall Design

This is a Phase 3, randomized, double-blind, active-controlled, parallel-group, multicenter study. A schematic of the study design is shown in Figure 7-1.

In the TEZ/IVA Run-in Period, all subjects will receive TEZ 100 mg once daily (qd)/IVA 150 mg every 12 hours (q12h). Following completion of the TEZ/IVA Run-in Period, approximately 100 subjects will be randomized (1:1) to the TC arm or TEZ/IVA arm for the Treatment Period. The planned dosages for the Treatment Period are shown in Table 7-1.

[figure not shown]
Table 7-1 Treatment Period Arms and Dosages

Treatment Arm	VX-445 Dosage	TEZ Dosage	IVA Dosage
VX-445/TEZ/IVA	200 mg qd	100 mg qd	150 mg q12h
TEZ/IVA	0 mg	100 mg qd	150 mg q12h

IVA: ivacaftor; q12h: every 12 hours; qd: once daily; TC: triple combination; TEZ: tezacaftor

All visits will occur within the windows specified. Please refer to the Table 3-1 and Table 3-2 of the CSP for more details about study visits and assessments.

Figure 7-1 Schematic of the Study Design

IVA: ivacaftor; N: number of subjects; TC: triple combination; TEZ: tezacaftor

Note: The Safety Follow-up Visit is not required for subjects who complete the Week 4 Visit and have enrolled in an open-label study within 28 days after the last dose of study drug (Section 9.1.4 of the CSP).

7.2 Sample Size and Power

The primary efficacy endpoint is the absolute change in ppFEV₁ from baseline at Week 4. The primary null hypothesis to be tested is that the mean absolute change in ppFEV₁ from baseline at Week 4 is the same for the TC and TEZ/IVA treatment groups. The null hypothesis will be tested at a 2-sided significance level of 0.05.

Assuming a within-group SD of 7 percentage points and a 5% dropout rate at Week 4, a sample size of 50 subjects in each treatment group for a total of 100 subjects will have approximately 93% power to detect a difference of 5.0 percentage points for the mean absolute change in ppFEV₁ from baseline at Week 4 between the 2 treatment groups, based on a 2-sided 2-sample *t*-test at a significance level of 0.05 using the [REDACTED].

7.3 Randomization

Randomization will be stratified by ppFEV₁ determined during the TEZ/IVA Run-in Period (Day -14 assessment; <70 versus ≥70) and age at the Screening Visit (<18 versus ≥18 years of age). If the Day -14 ppFEV₁ value is not valid or not available, the most recent available ppFEV₁ value before date of randomization will be used for stratification.

7.4 Blinding and Unblinding

Refer to the CSP Section 10.7 for details.

8 ANALYSIS SETS

The following analysis sets are defined: All Subjects Set, Full Analysis Set, Safety Set for the Run-in Period and Safety Set for the Treatment Period.

8.1 All Subjects Set

The **All Subjects Set** will include all subjects who are randomized or receive at least 1 dose of study drug. This analysis set will be used for all individual subject data listings and disposition summary tables, unless otherwise specified.

8.2 Full Analysis Set

The **Full Analysis Set (FAS)** will include all randomized subjects who carry the intended *CFTR* allele mutation and receive at least 1 dose of study drug in the Treatment Period. The FAS will be used to summarize subject demographics and baseline characteristics, and for all efficacy analyses in which subjects will be analyzed according to their randomized treatment group, unless otherwise specified.

8.3 Safety Set

The **Safety Set for the Run-in Period** will include all subjects who receive at least 1 dose of TEZ/IVA in the Run-in Period. This safety set will be included in individual subject data listings, unless otherwise specified.

The **Safety Set for the Treatment Period** will include all subjects who receive at least 1 dose of study drug in the Treatment Period. This safety set will be used for all safety analyses in which subjects will be analyzed according to the treatment they receive, unless otherwise specified.

9 STATISTICAL ANALYSIS

9.1 General Considerations

The Schedule of Assessments is provided in Section 3 of CSP. The precision standards for reporting safety and efficacy variables are provided in an internal Biometrics document that specifies the programming rules including the precision for derived variables.

Continuous variables will be summarized using the following descriptive summary statistics: the number of subjects (n), mean, SD, median, minimum value (min), and maximum value (max).

Categorical variables will be summarized using counts and percentages. Percentages will be presented to 1 decimal place.

Baseline value, unless otherwise specified, is defined as the most recent non-missing measurement (scheduled or unscheduled) collected before the first dose of study drug in the Treatment Period.

Absolute change from baseline will be calculated as post-baseline value – baseline value.

Relative change from baseline will be calculated as (post-baseline value – baseline value)/baseline value.

The **Treatment-emergent (TE) Period for the Run-in Period** will be from the first dose of study drug in the Run-in Period to

- 1) for subjects who complete the run-in period and continue to the Treatment Period, the first dose of study drug in the Treatment Period, or

- 2) for subjects who do not continue to the Treatment Period, either 28 days after the last dose date of study drug in the Run-in Period, or to the completion of study participation date, whichever occurs first.

The **TE Period for the Treatment Period** will include the time from the first dose date of study drug in the Treatment Period (TC or placebo + TEZ/IVA) to 28 days after the last dose of the study drug or to the completion of study participation date, whichever occurs first.

Unscheduled visits: Unscheduled visit measurements will be included in analysis as follows:

- 1) In scheduled visit windows per specified visit windowing rules
- 2) In the derivation of baseline and last on-treatment measurements
- 3) In the derivation of maximum and minimum values during TE period, and maximum and minimum change from baseline values during TE period for safety analyses
- 4) In individual subject data listings as appropriate

Visit windowing rules: The analysis visit windows for protocol-defined visits are provided in [Appendix A](#).

Incomplete/missing data will not be imputed, unless specified otherwise.

Outliers: No formal statistical analyses will be performed to detect or remedy the presence of statistical outliers, unless specified otherwise.

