### 9.1.2 Tezacaftor/Ivacaftor Run-in Period

The TEZ/IVA Run-in Period has a 4-week duration and is designed to establish a reliable on-treatment (TEZ/IVA) baseline for the Treatment Period. The first dose of open-label TEZ/IVA will be administered at the Day -28 Visit. The last dose of open-label TEZ/IVA will be administered in the evening on Day -1 (1 day before the Day 1 Visit).

On Day -14, spirometry and SwCl will be assessed. The Day -14 spirometry assessment will be used for stratification of randomization ([Section 9.2](#)).

Subjects who prematurely discontinue study drug treatment during the Run-in Period will not be randomized or participate in the Treatment Period ([Section 9.1.5.1](#)).

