## 9.3 Rationale for Study Design and Study Drug Regimens

### 9.3.1 Study Design

This Phase 3 study will assess the efficacy, PD, safety, and PK of VX-445/TEZ/IVA TC therapy in subjects with CF who have an F/F genotype.

A randomized, double-blind, controlled study design was selected to ascertain the effects of VX-445/TEZ/IVA while avoiding observer bias. TEZ/IVA is considered an appropriate active control since the efficacy and safety of TEZ/IVA in F/F subjects have been demonstrated in Study VX14-661-106 (Study 661-106). Study 661-106 met its primary endpoint of absolute change in ppFEV1 through Week 24, with a 4.0 percentage point treatment difference between TEZ/IVA and placebo. In Study 661-106, TEZ/IVA was well tolerated and no safety concerns attributable to TEZ/IVA were identified.

A 4-week TEZ/IVA Run-in Period was incorporated into this study to establish a reliable on-treatment (TEZ/IVA) baseline for comparison during the Treatment Period.

The study will have a 4-week treatment duration because previous studies of CFTR modulators (IVA, LUM/IVA, and TEZ/IVA) have demonstrated that efficacy related to lung function (ppFEV1) can be reliably established using an endpoint at Week 4. In these studies, rapid improvements in ppFEV1 are observed by Day 15, with a separation between the active treatment and placebo groups that is sustained through 24 weeks of treatment. These studies were conducted in patients with different genotypes, baseline ppFEV1, and age groups, using CFTR modulators that had different magnitudes of response.

The extent of response to CFTR modulator treatment may depend on the subject's ppFEV1 value (an index of disease severity) before the start of TC study drug dosing. Some subjects in this study may be receiving treatment with LUM/IVA or TEZ/IVA at Screening, while some subjects may not be receiving treatment with CFTR modulators. Therefore, randomization will be stratified by ppFEV1 value determined during the TEZ/IVA Run-in Period after at least 13 days of TEZ/IVA (Day -14 assessment). Randomization will also be stratified by age at screening. This will ensure a balanced evaluation of adult and pediatric subjects.

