## **12.3 Statistical Analysis**

### **12.3.1 General Considerations**

**Continuous variables** will be summarized using the following descriptive summary statistics: the number of subjects (n), mean, SD, median, minimum value (min), and maximum value (max). The precision of the measurement for each continuous variable will be specified in the SAP. Unless otherwise specified, min and max values will be reported with the same precision as the units of the raw data. The mean, median, and SD will be reported to 1 additional decimal place. Any values that require a transformation to standard units (metric or SI) will be converted with the appropriate precision.

**Categorical variables** will be summarized using counts and percentages. Percentages will be presented to 1 decimal place.

The **baseline value**, unless otherwise specified, will be defined as the most recent non-missing measurement (scheduled or unscheduled) collected before the first dose of study drug in the Treatment Period (i.e., the Day 1 Visit). For ECG, baseline will be defined as the most recent pretreatment measurement (or the average of triplicate measurements, if the most recent pretreatment measurement is obtained in triplicate) before the first dose of study drug in the Treatment Period (i.e., the Day 1 Visit).

**Absolute change** from baseline will be calculated as post-baseline value – baseline value.

The **Treatment-emergent (TE) Period for the Run-in Period** will be from the first dose date of study drug in the Run-in Period to (1) the first dose date of study drug in the Treatment Period for subjects who complete the Run-in Period and continue to the Treatment Period, or (2) 28 days after the last dose date of study drug in the Run-in Period or to the completion of study participation date, whichever occurs first, for subjects who do not continue to the Treatment Period (e.g., subjects who do not meet the conditions to enter the Treatment Period).

The **TE Period for the Treatment Period** will include the time from the first dose date of study drug in the Treatment Period (TC or placebo + TEZ/IVA) to 28 days after the last dose of the study drug or to the completion of study participation date (as defined in [Section 9.1.7](#)), whichever occurs first.

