9.3.2.2 Analysis Method

Absolute change in SwCl from baseline at Week 4:

Analysis of absolute change from baseline in sweat chloride will be based on an MMRM similar to the primary analysis of the primary efficacy variable. The model will include treatment, visit, and treatment-by-visit interaction as fixed effects with continuous baseline ppFEV₁, and age at screening (<18 versus ≥18 years of age) as covariates.

Absolute change in CFQ-R respiratory domain score from baseline at Week 4:

[figure not shown]
Analysis of absolute change from baseline in CFQ-R respiratory domain score will be based on an MMRM similar to the primary analysis of the primary efficacy variable. The model will include treatment, visit, and treatment-by-visit interaction as fixed effects with continuous baseline ppFEV₁, and age at screening (<18 versus ≥18 years of age) as covariates.

The LS mean (SE) of the within-treatment group change from baseline at each post-baseline visit up to Week 4 along with the 95% CI will be estimated from the corresponding MMRM. The LS mean (SE) of the treatment difference between VX-445/TEZ/IVA and TEZ/IVA at each post-baseline visit will be provided along with the corresponding 95% CI and *P* value. The LS mean (SE) at each visit will also be plotted by treatment group. In addition, the post-baseline raw values and the absolute change from baseline at each post-baseline visit up to Week 4 will be summarized descriptively (n, mean, SD, median, minimum, and maximum).

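### Does an open-ended baseline rule, which can make a pre-run-in Screening score the CFQ-R baseline, require a count or a sensitivity analysis in the SAP?

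*SAP*

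**What the plan says.** SAP 9.1 defines baseline as "the most recent non-missing measurement (scheduled or unscheduled) collected before the first dose of study drug in the Treatment Period". Protocol 12.3.1 gives the same rule. SAP Table 12-1 (Appendix A) sets the CFQ-R baseline window at study day 1 or earlier, with no lower end.

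Protocol Table 3-1 schedules CFQ-R at Screening, and Table 3-2 schedules it next on Day 1. Lung function and sweat chloride have an extra value in between: "On Day -14, spirometry and SwCl will be assessed" (Protocol 9.1.2). The same section says that the run-in is "designed to establish a reliable on-treatment (TEZ/IVA) baseline for the Treatment Period".

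The CFQ-R model in SAP 9.3.2.2 adjusts for baseline ppFEV1 and age group; baseline CFQ-R is not listed. Its outputs include "The LS mean (SE) of the within-treatment group change from baseline at each post-baseline visit up to Week 4", with a 95% CI, and the treatment difference at each visit. Under SAP 9.3.2.3 the between-arm CFQ-R comparison at Week 4 is tested last in the hierarchy. SAP 9.2.2 summarizes baseline CFQ-R only as a continuous variable. The only sensitivity analysis, SAP 9.3.1.4, concerns missing Week 4 ppFEV1.

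**The concern.** The run-in exists so that every subject's change is measured from a state on TEZ/IVA. A Screening score does not guarantee that state. Protocol 9.3.1 notes that some subjects may be on LUM/IVA or TEZ/IVA at Screening, while "some subjects may not be receiving treatment with CFTR modulators". A fallback baseline would therefore mean different things in different subjects. Because baseline CFQ-R is not a covariate, whatever happened to the score during the run-in passes in full into the change score.

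CFQ-R is the exposed endpoint. Spirometry and sweat chloride lose their on-treatment baseline only if both Day 1 and Day -14 fail; for CFQ-R the loss of Day 1 is enough unless an unscheduled run-in score exists. At stake would be the meaning of the within-arm CFQ-R change and some precision in a key secondary comparison. The SAP text provides no count from which a reader could see how many subjects are concerned.

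**Working it through.** **The plan's own figure.** SAP 7.2 states about 93% power for ppFEV1 with 50 per arm, SD 7, difference 5.0 and 5% dropout. With 50 × 0.95 = 47.5 per arm, the noncentrality is 5 / (7 × √(2/47.5)) = 3.48. A two-sided t-test at 0.05 then has 93.1% power (92.9% at 47 per arm, 93.4% at 48). The figure reproduces, and the baseline question does not affect it.

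**Age of a fallback score.** The Screening Period runs from Day -56 to Day -29, so the score is 29 to 56 days older than Day 1. With the two-week extension in Protocol 9.1.1.3 it can be 56 + 14 = 70 days older.

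**How many subjects.** The documents give no rate of missing Day 1 scores. Assume each visit's value is missing independently with probability p, and that no unscheduled run-in score exists.

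| p | CFQ-R fallback per 100 (100p) | Spirometry or SwCl fallback per 100 (100p²) |
|---|---|---|
| 2% | 2 | 0.04 |
| 5% | 5 | 0.25 |
| 10% | 10 | 1.0 |

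**Within-arm CFQ-R change.** If a fraction f of an arm falls back and the mean run-in shift is d, the arm's mean change moves by f × d. The documents give no d; assume -4 to +8 points.

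- f = 5%, d = 4: 0.05 × 4 = 0.20
- f = 10%, d = 8: 0.10 × 8 = 0.80
- f = 10%, d = -4: 0.10 × (-4) = -0.40

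**Between-arm difference, expectation.** The baseline is fixed before the first randomized dose. Protocol 9.1.3 allows randomization on Day -1, so allocation may precede the Day 1 questionnaire, but the trial is blinded. The expected fallback fraction and shift are therefore the same in both arms and cancel.

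**Between-arm difference, chance imbalance.** Three more fallback subjects in one arm of 50 move the estimate by 3/50 × d, which is 0.12, 0.30 or 0.48 points for d = 2, 5 or 8. An imbalance of three or more has probability of about 2%, 7% or 24% if 1%, 2% or 5% of Day 1 scores are missing. With an assumed SD of change of 17, the standard error of the difference is 17 × √(2/50) = 3.40. The largest of these moves is 0.48/3.40 = 14% of one standard error. It is ordinary sampling variation, which the model's standard error already covers.

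**Precision if the subjects are kept.** With SD of change s and extra noise SD τ in fallback scores, the standard error is multiplied by √(1 + [f(1−f)d² + fτ²]/s²).

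- f = 5%, d = 4, s = 15, τ = 10: √(1 + 5.76/225), or +1.3%
- f = 10%, d = 8, s = 15, τ = 10: √(1 + 15.76/225), or +3.4%
- f = 10%, d = 8, s = 17, τ = 10: √(1 + 15.76/289), or +2.7%

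A simulation of the last case (20,000 trials, 50 per arm, no true difference) gave a mean difference of -0.02, a standard error of 3.49 against 3.40 without fallback, and a within-arm shift of 0.81. This agrees with the algebra.

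**Precision if the subjects are excluded.** The multiplier is √(1/(1−f)): +1.0%, +2.6% and +5.4% at f = 2%, 5% and 10%. At 5% and 10% this exceeds the cost of keeping them in the two s = 15 cases above.

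**ppFEV1.** Protocol 9.3.1 cites an earlier trial "with a 4.0 percentage point treatment difference between TEZ/IVA and placebo". Taken as a stand-in for the run-in shift, one affected subject moves an arm's raw mean by 4.0/50 = 0.08 points, or 0.08/5.0 = 1.6% of the planning difference. This is only a rough guide: the 4.0 is a through-Week-24 contrast with placebo, and the primary model adjusts for baseline ppFEV1, so the adjusted effect would differ.

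**The case for a change.** The strongest argument for acting is that smallness rests on assumed rates and shifts, and that nothing in the SAP text would confirm it after the fact. CFQ-R is a key secondary endpoint, the within-arm change with its CI will be reported, and a count by arm costs one table row and no new data.

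The factual part stands: the rule is open below, CFQ-R has no scheduled on-run-in fallback, and the SAP text plans no such count. Four points weaken the rest.

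- The higher missing rates look unlikely. A subject in the FAS has taken randomized drug. Day 1 is a clinic visit, CFQ-R comes before every other assessment, and the morning dose is given on site after the predose assessments (Protocol 3, 9.6.1 and 11.6.2). A domain is still scored unless more than half of its items are missing (SAP 9.3.2.1). Subjects without a validated translation complete no CFQ-R, so they have no Screening score to fall back on.
- A large shift is not expected in everyone. Protocol 9.5 lets subjects stay on the sponsor's modulators through Screening without a washout; for those already on TEZ/IVA, the Screening score is itself an on-TEZ/IVA score.
- Re-running the CFQ-R model without the affected subjects whenever there is even one would be out of proportion. For missing Week 4 data on the primary endpoint, the SAP's own trigger is at least 10% in any arm.
- The document calls itself SAP (Methods), and its table shells are not shown. One can say that the text plans no count, but not that no output will reveal one.

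A count by arm of CFQ-R baselines taken before Day -28 is a harmless optional reporting note. An analyst can make it from visit dates already collected.

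**Conclusion.** No change to the plan is needed, because none would bring a gain. The baseline rule is the same in the protocol and the SAP, and it keeps subjects in the analysis who would otherwise have no CFQ-R change score. The tested quantity, the between-arm difference at Week 4, has zero expected bias and no type I error inflation. This rests on the blind and on the baseline being fixed before randomized dosing.

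What remains is a possible distortion of a descriptive within-arm mean. The documents do not allow its size to be estimated: the -0.4 to +0.8 points and the 0-3.4% rise in standard error both come from assumed missing rates, shifts and SDs, and their ends require 10% of Day 1 scores to be missing. If Day 1 CFQ-R is complete, every effect is zero. For ppFEV1 and sweat chloride the Day -14 value makes the matter negligible. A count row and a descriptive re-run outside the hierarchy would leave every planned test, estimate and conclusion as it is.

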9.2 Background Characteristics

9.2.1 Subject Disposition

A disposition table will be provided for the Run-in Period with the following categories:

- All Subjects Set
- Safety Set for the Run-in Period

The number and percentage (based on Safety Set for the Run-in Period) of subjects in each of the following disposition categories will be summarized:

- Prematurely discontinued treatment before randomization and the reason for treatment discontinuation
- Prematurely discontinued study before randomization and the reason for study discontinuation

A separate disposition table will be provided for the Treatment Period with the following categories:

- Full Analysis Set
- Safety Set for the Treatment Period
- Randomized
- Randomized but not dosed in the Treatment Period
- Randomized or dosed in the Treatment Period

The number and percentage (based on FAS) of subjects in each of the following disposition categories will be summarized by treatment group and overall:

- Completed study drug treatment
- Prematurely discontinued treatment and the reason for discontinuation (i.e., discontinued all study drugs)
- Completed study
- Prematurely discontinued the study and the reason for discontinuation
- Rollover to the open-label study

A listing will be provided for subjects who discontinued treatment (including both the Run-in Period and Treatment Period) or who discontinued study with reasons for discontinuation.

9.2.2 Demographics and Baseline Characteristics

Demographics and baseline characteristics will be summarized based on the FAS, and presented by treatment group and overall, as applicable.

Demographic data will include the following:

- Age at baseline (in years)
- Sex (female and male)
- Ethnicity (Hispanic or Latino, not Hispanic or Latino, and not collected per local regulations)
- Race (White, Black or African American, Asian, American Indian or Alaska Native, Native Hawaiian or Other Pacific Islander, and not collected per local regulations)
- Geographic region (North America, Europe)

Baseline characteristics will include the following:

- Weight (kg)
- Height (cm)
- BMI (kg/m²)

Stratification categories will include the following:

- Age at Screening Visit (<18, ≥18 years)
- ppFEV₁ at Day -14 (<70, ≥70)

Disease characteristics will include the following:

- ppFEV₁ at baseline (<40, ≥ 40 to <70, ≥70 to ≤90, and >90)
- ppFEV₁ at baseline (continuous)
- Sweat chloride at baseline (continuous)
- CFQ-R respiratory domain score at baseline (continuous)
- Prior use of dornase alfa before first dose of study drug in the Treatment Period (Yes, No)

- Prior use of azithromycin before first dose of study drug in the Treatment Period (Yes, No)
- Prior use of inhaled antibiotic before first dose of study drug in the Treatment Period (Yes, No)
- Prior use of bronchodilator before first dose of study drug in the Treatment Period (Yes, No)
- Prior use of inhaled bronchodilator before first dose of study drug in the Treatment Period (Yes, No)
- Prior use of inhaled hypertonic saline before first dose of study drug in the Treatment Period (Yes, No)
- Prior use of inhaled corticosteroids before first dose of study drug in the Treatment Period (Yes, No)
- Infection with *Pseudomonas aeruginosa* within 2 years prior to screening (Positive, Negative)

In addition, data listings will also be provided for:

- Informed consent;
- Inclusion/Exclusion criteria violation for subjects with any such violations.

